shown reduced length of intubation and accelerated functional recovery. In most studies, stimulation was applied to the lower extremity muscles bilaterally, generally to the quadriceps, and occasionally also to the hamstrings and/or calves, and in one study to the biceps brachii of the upper extremities. Stimulation was applied for 30 to 60 minutes/day, between 3x/week to twice/day for up to 14 days or until ICU discharge, whichever came first, with sufficient current amplitude to produce a muscle contraction.

Recent meta-analyses support that electrical stimulation results in positive outcomes in critically ill patients. These positive outcomes include accelerated recovery of, or better preservation of, muscle strength after cardiothoracic surgery (Fischer et al. 2016) and, in one study, the weaning period was statistically significantly shorter in patients undergoing electrical stimulations as compared to the control group [1 (0 to 10) days vs. 3 (0 to 44) days, respectively, median (range), P = 0.003], and activity limitations were reduced reflected by increased 6 minute walk test distance, and the average days to achieve transfer from the bed to the chair was reduced from 14.33 days to 10.75 days (Routsi 2010, Burke et al. 2016). Similar outcomes, including increased strength, VO2 max, and 6-minute walk test distance, as well as improved mood and quality of life, have been demonstrated in response to lower extremity electrical stimulation in patients with heart failure or other advanced diseases (Gomes Neto et al. 2016, Jones et al. 2016). Sepsis, edema, and receipt of vasopressors is associated with lower likelihood of response to this intervention (Segers 2014). Overall, these studies support that electrical stimulation can improve outcomes, including reducing duration of ventilation and accelerating recovery of functional mobility, in appropriately selected critically ill patients and in those with advanced systemic disease

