#### **Group Comparisons**

The study team statistician will analyze the data, and will be blinded to treatment assignment ("Group A" and "Group B", instead of "E-Stim Group" "Historical Controls"). Descriptive statistics will be used to quantify feasibility. Mean length of stay and mean duration of intubation will be compared between the e-stim group and the historical controls using a t-test. If necessary, a linear regression model for length of stay and/or intubation duration will be used to compare between groups while controlling for the potential confounding of covariates. A Wilcoxon rank-sum test will be used to compare the exploratory functional outcome measures between groups, as the mRS and GOSE are both ordinal scales.

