## **Power Calculation**

We plan a future trial to determine the efficacy of electrical stimulation to reduce days of mechanical ventilation by 30% (from 10 days to 7 days, observed in the Routsi study). Estimated sample sizes for a two-sample means test (Satterthwaite's t test) assuming unequal variances, with an 80% power to detect a 30% difference in days of mechanical ventilation with a significance level of p=0.05, would require 113 patients in each group (for a total of 226 subjects). In order to prepare for this future RCT, we propose a pilot trial of 45 subjects (20% of the full sample size), with 22 patients in the intervention group (e-stim) and 23 historical controls.

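### ICU stay and intubation days are analysed only on the raw mean scale in about 22 patients per group, so one very long stay can noticeably move the effect size and SD handed to the later RCT

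*Combined protocol and SAP*

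**What the plan says.** Under Group Comparisons in Section 8, "Mean length of stay and mean duration of intubation will be compared between the e-stim group and the historical controls using a t-test". The one fallback, conditional on the team finding it needed, is a covariate-adjusted linear model for the same outcomes. No transformation is mentioned. Rank methods appear only for the functional scales: "A Wilcoxon rank-sum test will be used to compare the exploratory functional outcome measures between groups".

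The Power Calculation plans the pilot "with 22 patients in the intervention group (e-stim) and 23 historical controls". It sets the future target as to "reduce days of mechanical ventilation by 30% (from 10 days to 7 days", and sizes the RCT by comparing two group averages ("Satterthwaite's t test) assuming unequal variances, with an 80% power to detect a 30% difference in days of mechanical ventilation"), giving 113 per group. No SD is stated.

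The Background reports weaning times from one cited trial as "1 (0 to 10) days vs. 3 (0 to 44) days, respectively, median (range), P = 0.003". Section 2 limits the intubation comparison to patients who were intubated, and gives the pilot's purpose as estimating the effect size for the RCT. Section 4 and the Historical Controls part of Section 6 say that the research team will receive only means for the controls.

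**The concern.** Days in ICU and days intubated cannot be negative and often have a long right tail. In a group of 22 or 23, a raw mean and SD then depend heavily on the one or two longest stays. The plan recognises that mRS and GOSE do not suit a t-test, but makes no comparable provision for days and has no check on how far one patient drives the result. This matters more than usual because the estimate is itself the product of the pilot: an unstable mean difference and SD would pass directly into the sample size of the RCT.

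**Working it through.** **Inputs.** Means of 10 and 7 days, a 3-day target, 80% power, alpha 0.05 and 113 per group (Power Calculation); 22 and 23 patients (same place); a 44-day maximum and a median of 3 (Background). Assumptions: two-sided alpha, and the distribution shapes named below.

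**1. The plan's 113 and the SD behind it.** The normal approximation is n = 2·SD²·(1.960 + 0.842)²/3². Solving for SD gives √(113 × 9/2)/2.802 = 22.55/2.802 = 8.05. A search with the Satterthwaite t-test returns 113 at SDs of 8.0/8.0, and also at 9.3/6.4 and 10/5.2. So 113 is reproducible only with a back-solved SD near 8. (A one-sided alpha would imply about 9.1.)

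**2. What that SD says about shape.** A normal distribution with mean 10 and SD 8 puts Φ(−10/8) = 11% of patients below zero days. With mean 7 and SD 8 it is Φ(−7/8) = 19%. Neither is possible, so an SD of this size implies right skew.

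**3. One extreme patient.** Shift in a group mean = (x − replaced value)/n.
- 44 days in place of 10: 34/22 = 1.55 days (52% of 3) or 34/23 = 1.48 days (49%).
- If only 12 patients in a group are intubated (assumed): 34/12 = 2.8 days (94%).

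**4. The typical longest patient.** Lognormal stays, mean 10, n = 23. Shift on deletion = (longest − mean of the other 22)/23.

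| Coefficient of variation | Median shift (days) | Share of samples with shift ≥ 1.5 days |
|---|---|---|
| 0.8 | 0.89 | 15% |
| 1.1 | 1.19 | 34% |

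The median shift is thus 30% to 40% of the 3-day target.

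**5. Stability of the variance.** For the same shape with coefficient of variation 0.93, the ratio of estimated to true variance has a 10th to 90th percentile range of 0.30 to 1.91 on the raw scale (median 0.71), against 0.64 to 1.40 on the log scale (median 0.97). Sample size is proportional to variance. With the 3-day difference held fixed and the same ratio in both groups, 113 would become 113 × 0.30 = 34 to 113 × 1.91 = 216, with a median of 113 × 0.71 = 80.

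**6. False positives.** Simulated type I error of the raw t-test at 22 vs 23 under lognormal data was 4.4% (SD 8) and 3.9% (SD 10).

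**7. Does the log scale estimate the same effect?** For lognormal data, geometric mean = m/√(1 + (s/m)²). For means of 10 and 7:
- SDs 8/8: 4.61/7.81 = 0.59, a 41% reduction.
- SDs 9.27/6.49 (equal coefficients of variation): 5.13/7.33 = 0.70.
- SDs 10/5.2: 5.62/7.07 = 0.79, a 21% reduction.

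**8. Power for 10 vs 7 days.** With lognormal data, 22 vs 23 and coefficients of variation of 0.8 to 1.1: t-test 0.19 to 0.31, log scale 0.26 to 0.39, rank test 0.25 to 0.37. At 113 per group and 0.93: 0.83, 0.92 and 0.91. With gamma tails the order reverses: the log test loses about 3 to 5 points at pilot size and 10 to 23 points at 113 per group.

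**The case against.** The best defence is that this is a feasibility and estimation pilot, that the t-test holds its level, and that a difference in means is the quantity the planned RCT is sized on. All of that stands. The evidence of skew is also indirect: the 44-day value is a weaning time from a cited trial outside the Neuro ICU, and the SD of 8 is derived, not stated.

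Three stronger readings are tempting, and the documents do not support them.
- A reader might infer that the longest stay usually accounts for half the target effect. Longest stay divided by 23 does come to about 1.3 to 1.6 days, but an average 10-day patient already contributes 10/23 = 0.43 days. The relevant quantity is the shift when the patient is removed, and that reaches 1.5 days in a minority of samples.
- A reader might infer that the t-test is invalid. The simulated type I error is below 5%.
- A reader might infer that log(days) should replace the raw comparison because the target is a 30% reduction. The target is a ratio of means. The geometric-mean ratio equals it only if the log-scale SDs are equal, and the Power Calculation assumes unequal variances. The gain in power also depends on the shape of the tail.

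A further objection is that both cited ranges start at zero, where the log is undefined. It has little force here: intubation days are analysed only in intubated patients, and enrolment starts on ICU day 2.

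**Conclusion.** The concern holds as a gap in robustness. With about 22 patients per group, and fewer for intubation, the only planned analyses of days are raw-scale ones, and the available figures suggest right skew. An extreme but cited value would move a group mean by about 1.5 days, half the 3-day target. The longest stay would typically move it by 0.9 to 1.2 days if stays are lognormal with a coefficient of variation of 0.8 to 1.1. The SD is affected too: under the lognormal assumption the median pilot understates the variance by about 30%. The consequence is an unstable basis for sizing the RCT. The half-target comparison applies strictly to ventilation days, since no target is given for length of stay. The pilot is not invalidated, and the raw mean difference need not be abandoned.

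**What to change.** - Keep the difference in means as the estimate that matches the means-based RCT, and report it with a bootstrap 95% CI.
- Pre-specify alongside it a Wilcoxon rank-sum test with medians and IQR, and a log-scale ratio of geometric means with 95% CI. State that this ratio equals the ratio of means only if the log-scale SDs are equal.
- Examine the RCT sample size under both the raw and the log-scale SD.
- Request de-identified patient-level control values from the ICU quality group. Rank and bootstrap analyses cannot be done from means. The t-test already needs a control SD and the covariate-adjusted regression needs individual values, so Section 4 and the Historical Controls text in Section 6 must be reconciled with Section 8 in any case.

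The cost is a wider data request, revised analysis wording and a few more results to report.

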## **Power Calculation**

We plan a future trial to determine the efficacy of electrical stimulation to reduce days of mechanical ventilation by 30% (from 10 days to 7 days, observed in the Routsi study). Estimated sample sizes for a two-sample means test (Satterthwaite's t test) assuming unequal variances, with an 80% power to detect a 30% difference in days of mechanical ventilation with a significance level of p=0.05, would require 113 patients in each group (for a total of 226 subjects). In order to prepare for this future RCT, we propose a pilot trial of 45 subjects (20% of the full sample size), with 22 patients in the intervention group (e-stim) and 23 historical controls.

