# 2. Objectives

The purpose of this pilot trial is to estimate the effect of electrical stimulation (e-stim) to the bilateral quadriceps on duration of intubation, intensive care unit (ICU) and hospital length of stay, and functional recovery in the Neuro ICU in comparison to historical matched controls. The objective of this initial pilot and feasibility study to estimate the effect size to power a future full scale randomized controlled trial of this intervention and to optimize study logistics for a future full scale trial. We propose the following specific aims:

**Specific Aim 1 - Feasibility:** Determine whether at least 80% of planned treatments can be performed as described, and that there is adequate patient population meeting inclusion criteria available for study

**Specific Aim 2 - Efficacy:** Evaluate efficacy of e-stim by comparing length of ICU stay (days from admission to "intermediate level of care" ordered in Epic) and duration of intubation (days) of subjects (for those who were intubated) to that of historical controls.

**Specific Aim 3 - Exploratory:** Evaluate functional recovery (measured by modified Rankin Scale [mRS] and Extended Glasgow Outcome Scale [GOSE] at Neuro ICU discharge) of subjects compared to that of historical controls.

**Hypothesis:** We hypothesize that e-stim treatment will be feasible in the Neuro ICU and will reduce the length of hospital stay and intubation and improve functional recovery.

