#### **Historical Controls**

The Neuro ICU administration maintains databases for the purpose of safety and quality improvement. We propose to query this existing database to identify patients cared for in the Neuro ICU during the year 2016 that possess similar demographics and illness characteristics as our inclusion criteria. The ICU quality group will abstract data for us. The research team will not have access to identifiable data for the historical controls—only means from the historical controls on data such as length of stay and hospital costs. The information will be extracted using automated means from this database and Epic to capture average length of stay and length of ventilator support for the purposes of comparison as "historical controls". We will not be performing individual chart review.

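### The figure of 23 historical controls comes only from the future trial's size, and no step says how the eligible 2016 patients become 23

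*Combined protocol and SAP*

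**What the plan says.** The number of controls appears in one place, the Power Calculation in Section 8. The future trial "would require 113 patients in each group (for a total of 226 subjects"), and from this "we propose a pilot trial of 45 subjects (20% of the full sample size"). The split between the groups is then given as "with 22 patients in the intervention group (e-stim) and 23 historical controls". No other reason for 23 is given.

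Elsewhere the comparator is described without a number:

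- Section 6, Historical Controls, plans a query of the quality database to "identify patients cared for in the Neuro ICU during the year 2016 that possess similar demographics and illness characteristics as our inclusion criteria". Extraction is automated, there is no individual chart review, and the research team receives only means.
- Section 4 and Section 5a also refer to pooled, de-identified patients from the quality databases. Section 5a fixes the 22 e-stim patients but gives no control count.
- Section 2 places the e-stim results "in comparison to historical matched controls".
- The end of Section 3 says the comparison will take account of age, sex, illness severity, comorbidities and other predictors of length of stay. Section 8 lists covariates and allows regression adjustment.

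The plan thus states a source year, a similarity filter and a set of comparison factors. It gives no matching ratio, caliper, algorithm or sampling rule by which the patients who pass the filter become 23.

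**The concern.** A main purpose of the pilot is to estimate an effect size for a later randomised trial, so both the precision of the comparison and the way the controls are chosen matter.

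Equal groups make sense when each control costs as much to recruit as each treated patient. Here a control costs a line in an automated query. If more than 23 patients qualify, stopping at 23 gives up information that is already on file.

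The choice itself is the more serious matter. The outcomes of 2016 patients are already recorded. If the Power Calculation is followed and the pool is larger than 23, the group abstracting the data must decide which patients to keep, and nothing in the plan requires that decision to be made without sight of outcomes. Even an honest random draw moves the control mean by an amount that is large beside the target effect.

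**Working it through.** **Inputs from the plan (Section 8, Power Calculation)**

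- Target: "reduce days of mechanical ventilation by 30% (from 10 days to 7 days"), a difference of 3 days.
- Power: "80% power to detect a 30% difference in days of mechanical ventilation".
- Test level: "with a significance level of p=0.05". Sidedness is not stated; two-sided is assumed.
- Future trial: 113 per group, 226 in total. Pilot: 22 e-stim and 23 controls.
- Not stated: the SD and the number of eligible 2016 patients.

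**Step 1. Reproduce the pilot size.** 0.20 × 226 = 45.2, rounded to 45; 45 − 22 = 23. The figure reproduces, and it carries no information about the database.

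**Step 2. Back-solve the SD.** From n = 2 × (1.96 + 0.84)² × SD² / 3² with n = 113, SD = 3 × √(113/2) / 2.80 ≈ 8.0 days. A t-based calculation gives 7.98 to 8.01. A one-sided test would imply about 9.1. The plan assumes unequal variances, so 8 days is the root mean square of the two SDs. It belongs to ventilation days; using it for length of stay is a further assumption.

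**Step 3. Precision with m controls, equal SDs.** SE = SD × √(1/22 + 1/m). The 95% half-width is 1.96 × SE.

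| Controls m | SE at SD 8 (days) | Fall in SE against 23 | 95% half-width (days) |
|---|---|---|---|
| 23 | 2.39 | – | 4.68 |
| 50 | 2.05 | 14% | 4.01 |
| 100 | 1.88 | 21% | 3.69 |
| 200 | 1.80 | 25% | 3.52 |
| unlimited | 1.71 | 28.5% | 3.34 |

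The percentages do not depend on the value of the SD, but they do need the two SDs to be equal. The ceiling is 1 − √(1/22) / √(1/22 + 1/23) = 1 − 0.2132/0.2982 = 28.5%. With assumed SDs of 7 (e-stim) and 9 (controls) it would be 1 − √[(49/22) / (49/22 + 81/23)] = 38%. With the SDs reversed it would be 1 − √[(81/22) / (81/22 + 49/23)] = 20%.

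Half-widths at other SDs, 23 against 200 controls: SD 5, 2.92 and 2.20 days; SD 10, 5.85 and 4.40; SD 12, 7.01 and 5.28.

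**Step 4. Dependence on which 23 are drawn.** For a simple random draw of 23 from M eligible patients, the SD of the control mean is (8/√23) × √[(M − 23)/(M − 1)].

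| Pool M | SD of the mean of 23 (days) | 95% range (days) |
|---|---|---|
| 50 | 1.24 | ±2.43 |
| 100 | 1.47 | ±2.88 |
| 200 | 1.57 | ±3.08 |
| very large | 1.67 | ±3.27 |

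The target effect is 3 days. A draw that is not random could move the mean further.

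**Step 5. Intubated patients only.** Section 2 limits the intubation comparison to those who were intubated, so its numbers are smaller. If, as an illustration, half of each group were intubated (11 and 12), the half-width at SD 8 would be 6.55 days, against 4.86 with 11 and 200.

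**The case against.** The best defence is that the number 23 stands only in the Power Calculation. Sections 4, 5a and 6 can be read as returning averages over everyone who passes the 2016 filter, which is close to what is asked for here. That reading is fair. It shows two descriptions that have not been reconciled, and the two give different comparators, so the text needs correcting either way.

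A reader might infer that the plan discards most qualifying controls. The documents do not support this: it would need more than 46 eligible patients, and the pool size is not given. The filter may be narrow, and if about 23 qualify, the precision gain disappears.

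A reader might also infer that the controls are taken by no rule at all. That too goes beyond the text, since a year, a similarity filter and comparison factors are stated. Only the last step, from eligible patients to 23, is absent.

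Three further objections stand as limits. First, the gain is bounded by the 22 e-stim patients: at SD 8, unlimited controls still leave about ±3.3 days around a 3-day target. Second, more controls do nothing about confounding between 2016 patients and later enrolees. Third, a larger query returned only as means could not feed the planned t-test, regression or rank-sum test. That is equally true of 23 controls, so the form of the control data has to change along with the number.

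**Conclusion.** The point holds as an unreconciled control count with a missing selection step, and as an inexpensive improvement to the design. It does not show that controls are certain to be thrown away.

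If more than 23 patients are eligible, following the Power Calculation forgoes a reduction in the SE of 14% to 25% for 50 to 200 controls, with a ceiling of 28.5%. These figures assume equal SDs. The larger consequence is discretion. At an SD of 8 days, a random choice of 23 moves the control mean with an SD of 1.24 to 1.67 days, roughly 40% to 55% of the 3-day target (1.24/3 and 1.67/3). This rests on a back-solved, two-sided SD for ventilation days and on assumed pool sizes of 50 and upward.

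**What to change.** 1. In the Power Calculation, replace the 23 with all 2016 patients who meet a written control definition. Build that definition from those Section 5b inclusion and exclusion criteria that the database can apply, and report the number eligible. The 45-subject total should no longer limit the controls.
2. If matching is kept, state a fixed 1:k algorithm on age, sex, APACHE II and diagnosis, run by the quality group without sight of outcomes. If it is not kept, remove the word from Section 2.
3. Align Sections 2, 4, 5a and 6 with the choice made.
4. Have the quality group supply de-identified rows. Failing that, n and SD with each mean would support the t-test, but not the regression or the rank-sum test. Amend the means-only statements in Sections 4 and 6 to match.

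The cost is protocol wording and a larger output from the same automated query, with no added participants, visits or consent. Groups of unequal size are no obstacle to the planned methods once the data in item 4 are available, but the sizes may tell the blinded statistician which group is Group A. Confounding from non-concurrent controls remains and should be stated as a limitation.

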# 9. Privacy, Confidentiality, and Data Security

Standard institutional practices will be followed as described by the OHSU Information Security Directives at the following link (http://www.ohsu.edu/xd/about/services/integrity/policies/ips-policies-info-sec-directiv.cfm#results) to maintain the confidentiality and security of data collected in this study. Study staff will be trained with regard to these policies.

To protect confidentiality, all hard-copy forms and identifying information will be kept in locked cabinets located within the offices of study personnel. These forms will be controlled and secured at all times by study personnel. All electronic data will be stored in a secure, password-protected web-based platform accessible to study team members only (RedCap).

Confidentiality will be assured by assigning patients unique study identification numbers rather than names or medical record numbers on all clinical research forms and other source documents. The identification numbers will not contain any part of the 18 HIPAA identifiers (initials, date of birth, medical record number, etc.) The key associating the codes and subjects' personally identifying information will be restricted to the PI and study staff. The key will be kept on a restricted OHSU network drive in a limited access folder.

All published results will exclude all identifying protected health information including names or initials of subjects, birth dates, medical record numbers, etc.

All adverse events and/or unanticipated problems related to the study evaluations or protocol will be reported in a timely fashion to the IRB. Reportable New Information (RNI) (information that meets the regulatory definition of an unanticipated problem involving risks to subjects or others or serious or continuing noncompliance) will be submitted to the IRB within 5 days of discovering the information.

When follow-up assessments are complete, research staff and biostatistical consultants will complete a comprehensive double entry procedure to verify overall data accuracy. All research personnel have completed updated and verified conflict of interest agreements with their respective institutions.

